#### **Study Design and Methods**

This is a randomized, controlled pilot study to be conducted at Mayo Clinic in Rochester, MN examining the effects of a health coaching intervention on the self-management ability of patients awaiting heart or lung transplant. The relationship between self-management and pre-transplant risk factors such as uncertainty, resilience, frailty, and affect will also be explored. Patients on the active or deferred waiting lists or with a waiting list status of "temporarily inactive" will be approached for recruitment in the Transplant Clinic at a routine clinical follow-up appointment (occurring every 1 to 3 months) or by phone or mail. All participants will complete a written consent form in person via email-PTRAX, phone or by mail. After consenting, patients will schedule a research visit to complete baseline measures including questionnaires, a hand grip strength test, a timed gait speed test over a distance of 15 feet, Short Physical Performance Battery (SPPB) and a 60-second body composition scan. A body composition analyzer (InBody 770) will be used to determine body composition (body mass, fat mass, and fat-free mass) via electrical impedance. Participants will also receive an activity monitor at their baseline visit to be worn for 5-7 days. In addition; participants will be given a pedometer to track their steps throughout the study. If participants are unable to schedule a research visit, they may be mailed the questionnaires or sent via Redcap (electronically) and activity monitor will be sent via the mail, which will be returned in postage-paid envelopes. Participants will be randomized to one of two groups while completing their baseline measures. Participants in one group will continue to receive the standard pre-transplant care for 12 weeks. Participants in the intervention group will receive a health coaching intervention in which they will be assigned a health coach trained in motivational interviewing who will call the patient weekly for 12 sessions for an approximately 30 minute intervention. Participants who miss a call will be allowed a make-up call with the goal of finishing 12 calls over a 16-week period. The health coaching calls will be recorded and externally monitored by an independent expert to assure treatment fidelity, and all recordings will remain private. In

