4. Body composition scan: Participants will stand on the InBody 770 body composition analyzer, which determines body composition by electrical impedance (i.e., sending an electrical signal through the body). Height, weight, BMI, skeletal muscle mass, percent body fat, and segmental lean mass will be recorded. Participants with a pacemaker, an implantable cardioverter-defibrillator (ICD), or an automated ICD (AICD) will not be able to complete this body composition scan. Those patients will have their height and weight collected. BMI will be calculated.

5. Activity monitoring: Participants will receive an Actigraph activity monitor to be worn on the wrist for 5-7 days. The activity monitors are capable of measuring the number of steps taken, the number of calories

burned, the intensity of physical activity, the amount of sedentary time, and other variables. Participants will receive a prepaid addressed envelope to return the activity monitor.

6. Center for Epidemiologic Studies Depression Scale (CES-D): Participants will answer 2 questions from the CES-D about their level of exhaustion.

7. Self-reported weight loss: Patients will be asked whether they intentionally lost 10 or more pounds within the last year. As available, weight changes in kg will also be abstracted from the medical record to trend the weight over the prior year's time.

8. Demographic information: Patients will be asked to self-report their sex, race, ethnicity, marital status, education level, and the relationship of their primary caregiver post-transplant.

9. Questionnaires:
Chronic Respiratory Questionnaire (lung disease only)
Kansas City Cardiomyopathy Questionnaire (heart disease only)
Mishel Uncertainty of Illness Questionnaire
Positive Affect Negative Affect Questionnaire (affect)
Perceived Stress Scale (stress)
PHQ 2 and GAD 2 (mood/affect)
RISC-10 (resilience)
Frailty Deficit Index (frailty)
SMAQ (adherence)
SMAS-30 (self-management)

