## Subject Information

Target accrual: 60 patients

Subject population: Patients on the heart and lung transplant waiting lists

Inclusion Criteria: Aged 18 or older, consenting to research, and listed (active and temporarily inactive) or deferred for lung or heart transplantation at Mayo Clinic in Rochester, MN

Exclusion Criteria: Patients will be excluded if ineligible for transplant, non-English speaking, non-verbal or extremely hard of hearing.

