Health Coaching to Improve Self-Management in Thoracic Transplant Candidates NCT03150095 5/09/2017

PI: [name] MD, Mayo Clinic Rochester, MN

ANALYSIS PLAN: Sample size: This is a pilot and feasibility study. However, to inform our enrollment we have made the following calculations. Change in SMAS-30. A sample size of 25 in each group will have 80% power to detect an effect size of 0.81 using a two-group t-test with a 0.05 two-sided significance level, where effect size is the end of study difference in means between the two groups relative to the SD of the end of study measures, after adjusting for baseline and other factors. From the literature, we estimate an unadjusted end of study SD for SMAS-30 of 8.5. Whereas we do expect our intervention to impact SMAS-30, it is our clinical impression that without intervention, patients tend to exhibit similar patterns over time. Therefore, we expect the between-person variability in SMAS-30 to be at least as large as the variability in assessing SMAS-30 for the same person at different time points. If these two sources of variability were the same then they would both have a SD of 6.0, in particular the end of study SD for SMAS-30 would be 6.0 or less. With this SD, we would have power to detect a difference of 0.81x6.0=4.9. Thus, this pilot study is reasonably powered. Allowing for a 20% withdrawal rate (primarily due to transplantation during intervention), we will aim for a sample size of 30 per arm. Analysis plan: Demographic characteristics will be summarized by mean, median, SD and range (continuous variables) and counts and percents (categorical variables). Our primary variable will be end of study SMAS-30 (adjusting for baseline), which we will analyze using analysis of covariance (ANCOVA), estimating between group differences. Subgroup analysis will be performed by sex, ethnicity, and race as feasible. A similar procedure to that described above will be employed to impute data if necessary. Missing data and end of study SDs for SMAS-30, adjusting for baseline, will guide analysis and power calculations for future R01 studies. Secondary Outcomes will examine between group differences of changes in gait speed, activity levels, body composition, weights, and RISC-10, PANAS, MUIS, FDI, SMAO, and KCCO or CRO measures to inform future R01 planning. A two-tailed p< 0.05 will be considered statistically significant.

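### Heart and lung candidates are pooled with no named stratification factor, and the SMAS-30 ANCOVA names no covariate beyond baseline: a small but cheaply avoided loss of balance and precision

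*Protocol*

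**What the plan says.** Two organ groups and three listing states are eligible. The protocol's Subject Information section gives "Subject population: Patients on the heart and lung transplant waiting lists" and admits those "listed (active and temporarily inactive) or deferred for lung or heart transplantation". On allocation, Study Design and Methods says only "Participants will be randomized to one of two groups while completing their baseline measures". It gives no ratio, sequence, blocking or stratification factor.

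The SAP's analysis text names a single covariate: "Our primary variable will be end of study SMAS-30 (adjusting for baseline), which we will analyze using analysis of covariance (ANCOVA". Its sample-size text, however, defines the effect size "after adjusting for baseline and other factors" and does not say what the other factors are. Subgroups are limited to demographics: "Subgroup analysis will be performed by sex, ethnicity, and race as feasible".

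Among the Study Measures, item 9 restricts the CRQ to lung disease and the KCCQ to heart disease. Item 4 restricts the body scan by implanted device: "Participants with a pacemaker, an implantable cardioverter-defibrillator (ICD), or an automated ICD (AICD) will not be able to complete this body composition scan". Study Design and Methods lists type of transplant and date of listing among the abstracted data. It does not list listing status. The SAP expects 20% withdrawal, mainly because of transplantation during the intervention.

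**The concern.** Organ is a division that the design itself recognises, because it assigns different quality-of-life instruments to the two groups. Organ may also relate to SMAS-30, gait and activity. Listing status plausibly affects the chance of transplantation during the 12 to 16 weeks, which is the SAP's main expected cause of withdrawal. Neither factor is named as a stratifier, covariate or subgroup.

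With 60 patients, an appreciable chance imbalance is possible. It would shift the observed SMAS-30 contrast in that one trial, and some explainable variance would stay in the error term. Both matter for the stated purpose of the pilot, which is to supply effect estimates and SDs for planning a larger study. The power statement and the analysis model also do not match while the other factors remain unnamed.

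**Working it through.** **1. The plan's own figures.** With 25 per arm, an effect of 0.81 SD and two-sided alpha 0.05, the noncentral t (48 df) gives 80.1% power, which reproduces the stated 80%. The SAP splits an unadjusted SD of 8.5 into two equal components: 8.5/√2 = 6.01, and 0.81 × 6.0 = 4.86, stated as 4.9. Two equal components imply a baseline to follow-up correlation of 36/(36 + 36) = 0.5, which is used below.

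**2. Chance of imbalance.** The organ mix is not in the documents, so it is assumed. With 30 heart and 30 lung patients and arms fixed at 30:30, the number of heart patients in one arm is hypergeometric(60, 30, 30). A 20-point difference in organ share means 18 against 12 or worse, and P(|k − 15| ≥ 3) = 0.196. Under simple randomisation, where arm sizes also vary, the chance of a difference of at least 20 points is 0.155.

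| Assumed minority organ share | Fixed 30:30 arms | Simple randomisation |
|---|---|---|
| 50% | 19.6% | 15.5% |
| 30% | 15.8% | 9.9% |
| 20% | 10.4% | 6.1% |

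**3. Shift in the planned ANCOVA.** Assume a within-organ SD of 1, a within-organ correlation of 0.5, and an organ difference D that is the same at baseline and follow-up. With organ shares of 0.6 and 0.4 in the two arms, let q = 0.6 × 0.4 × D² = 0.24D². The pooled within-arm slope on baseline is b = (0.5 + q)/(1 + q), and the shift is 0.2D(1 − b).

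- D = 0.25: b = 0.515/1.015 = 0.507; shift = 0.05 × 0.493 = 0.025 SD
- D = 0.5: b = 0.56/1.06 = 0.528; shift = 0.10 × 0.472 = 0.047 SD
- D = 1: b = 0.74/1.24 = 0.597; shift = 0.20 × 0.403 = 0.081 SD

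Taking 8.5 as the SD, these are about 0.2, 0.4 and 0.7 SMAS-30 points, or 4%, 8% and 14% of 4.9.

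**4. Precision.** With equal organ shares, let q = D²/4. Residual variance given baseline alone is (1 + q) − (0.5 + q)²/(1 + q). With organ added it is 1 − 0.5² = 0.75.

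- D = 0.25: 0.754 to 0.75, a reduction of 0.5%
- D = 0.5: 0.765 to 0.75, a reduction of 2%
- D = 1: 0.80 to 0.75, a reduction of 6%

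**5. Cost of the extra terms.** At 25 per arm and 0.81 SD, adding one covariate with no prognostic value leaves power at 80.1%. Adding two leaves 80.05% (80.12% with none).

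**6. Organ-specific questionnaires.** With a 50:50 mix and about 25 evaluable per arm, each questionnaire has roughly 12 to 13 per arm. The effect detectable with 80% power is then 1.15 to 1.20 SD. A chance split of 18:12 instead of 15:15 raises the variance of the comparison by (1/18 + 1/12)/(1/15 + 1/15) = 0.1389/0.1333, or about 4%. The small subset limits these comparisons far more than the uneven split does.

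**The case against.** The strongest reply is that an unstratified trial is not a biased one. Randomisation is valid in expectation, and the standard error already allows for chance imbalance. This stands. A reader might infer that organ confounds the results, but the documents support only chance imbalance and lost precision.

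Other stronger readings also fail:

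- A reader might take the shift as 0.2D, that is 0.05 to 0.20 SD, with a variance gain of up to 20%. Those figures describe an unadjusted contrast. The SAP adjusts for baseline, and baseline absorbs at least half of a stable organ difference. For secondary outcomes analysed as changes, a stable difference cancels. Organ matters there only if the two groups follow different courses, and the documents do not address that.
- Under simple randomisation, the chance that 30 heart patients split 18:12 or worse is 36%. That describes the split within one organ. It is not a 20-point imbalance between arms, for which the chance is 15.5%.
- Only two outcomes are organ-specific. Body composition is limited by implanted device.
- The SAP does not exclude further adjustment. It mentions other factors and leaves them unnamed.
- Pooled SDs contain organ heterogeneity whether or not the arms are balanced. Stratifying would not remove it, and a future trial with the same mix would need that SD.
- Unequal loss to transplantation through listing imbalance is plausible, but it cannot be sized. The documents give neither the listing mix nor transplant rates by status.

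The protocol's primary endpoint is also acceptability and feasibility, which organ imbalance barely affects. What remains is that a factor built into the measures, and already collected, is missing from both the allocation text and the model.

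**Conclusion.** The point holds as a modest, low-cost improvement. Neither organ nor listing status is named in the allocation or the analysis, and the SAP's power statement relies on adjustment factors that its analysis text does not specify.

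Under an assumed 30:30 organ mix, an organ imbalance of 20 points or more has a chance of about 20% (fixed arms) or 16% (simple randomisation), and less for more unequal mixes. Such an imbalance would shift the SMAS-30 contrast by about 0.025 to 0.08 SD, and adding organ would cut residual variance by about 0.5% to 6%. These sizes assume a within-organ correlation of 0.5, taken from the SAP's own equal-variance illustration, and a stable organ difference of 0.25 to 1 SD, which the documents do not give. The listing-status part is a reasoned argument without a figure.

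**What to change.** If randomisation is not finished, stratify it by organ in small permuted blocks. Do not cross organ with all three listing states: six cells would average 60/6 = 10 patients, or 5 per arm.

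Whether or not randomisation is finished, state in the SAP that organ (already abstracted as type of transplant) is a covariate in the SMAS-30 ANCOVA and in the secondary models that pool the organs. Record listing status at baseline as active versus deferred or temporarily inactive, and add it as a second covariate. Naming both also settles what the other factors in the sample-size text are.

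The cost is SAP wording, one recorded field, one or two degrees of freedom and, where still possible, a revised allocation list. The change does not solve missing outcomes caused by transplantation. That needs its own text, because the SAP's imputation sentence points back to a procedure that the document does not contain.

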## Study Measures:

Participants will complete the following testing, SPPB measures, and wear an Actigraph at baseline and after completing the intervention (or in an equivalent time-frame if a control patient).

1. Hand grip strength test: Hand grip strength will be measured using a Jamar Digital Hand Held Dynamometer. Participants will complete the grip strength test 3 times with their dominant hand. The 3 trials will be averaged and adjusted by sex and BMI using a normative table.

2. Gait speed test: The participant's gait speed will be measured using a stopwatch as the participant walks a distance of 15 feet at a self-selected walking speed. The average of 3 trials will be calculated and adjusted for sex and height. To determine the participant's SPPB score, the results of the gait speed test will be prorated for 4 meters (13.1 feet). The best of 3 trials will be used to calculate the participant's SPPB score.

3. Short physical performance battery (SPPB): The SPPB consists of a gait speed test over 4 meters (13.1 feet), timed repeated chair stands, and 3 balance tests.

a. Gait speed test: See #2.

b. Timed repeated chair stands: Participants will be asked if they feel safe to stand from a chair without the use of their arms and without assistance. If the participant feels safe to stand from a chair without the use of their arms and without assistance, they will be asked to complete 5 repeated chair stands. The participant's SPPB score will be determined by the time required to complete 5 repeated chair stands.

c. Balance testing: The participant's balance will be tested in side-by-side, semi-tandem, and tandem stands. In the side-by-side stand, participants will stand with their feet as close together as possible. In the semi-tandem stands, participants will stand with one heel touching the big toe of the opposite foot. In the tandem stands, participants will stand with the heel of one foot in front of the toes of the other foot (as if on a balance beam). Participants will be asked to hold each position for up to 10 seconds.

4. Body composition scan: Participants will stand on the InBody 770 body composition analyzer, which determines body composition by electrical impedance (i.e., sending an electrical signal through the body). Height, weight, BMI, skeletal muscle mass, percent body fat, and segmental lean mass will be recorded. Participants with a pacemaker, an implantable cardioverter-defibrillator (ICD), or an automated ICD (AICD) will not be able to complete this body composition scan. Those patients will have their height and weight collected. BMI will be calculated.

5. Activity monitoring: Participants will receive an Actigraph activity monitor to be worn on the wrist for 5-7 days. The activity monitors are capable of measuring the number of steps taken, the number of calories

burned, the intensity of physical activity, the amount of sedentary time, and other variables. Participants will receive a prepaid addressed envelope to return the activity monitor.

6. Center for Epidemiologic Studies Depression Scale (CES-D): Participants will answer 2 questions from the CES-D about their level of exhaustion.

7. Self-reported weight loss: Patients will be asked whether they intentionally lost 10 or more pounds within the last year. As available, weight changes in kg will also be abstracted from the medical record to trend the weight over the prior year's time.

8. Demographic information: Patients will be asked to self-report their sex, race, ethnicity, marital status, education level, and the relationship of their primary caregiver post-transplant.

9. Questionnaires:
Chronic Respiratory Questionnaire (lung disease only)
Kansas City Cardiomyopathy Questionnaire (heart disease only)
Mishel Uncertainty of Illness Questionnaire
Positive Affect Negative Affect Questionnaire (affect)
Perceived Stress Scale (stress)
PHQ 2 and GAD 2 (mood/affect)
RISC-10 (resilience)
Frailty Deficit Index (frailty)
SMAQ (adherence)
SMAS-30 (self-management)

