addition to the health coaching intervention, participants in the intervention group will also continue to receive standard pre-transplant care. After completion of the intervention, all participants will be asked to complete a follow-up research visit in which they will complete the questionnaires, hand grip strength test, timed gait speed test, SPPB, and bioelectrical impedance test a second time. All participants will also be asked to wear an activity monitor again for 5-7 days. At the end of the intervention, participants will be completed within 90 days of completing the study. Demographic data will be collected at the time of the initial questionnaires and verified with the follow-up questionnaires. If a participant leaves large sections or multiple pages of the questions or indicate that the questions were purposely left unanswered. Psychometric surveys will be stored in a locked cabinet. Data will be entered into a secure password-protected REDCap database. Questionnaire data, measurements, and abstracted data (age, type of transplant, 6 minute walking distance, race, ethnicity, psychological assessment information, marital status, height, weight, date of listing, primary diagnosis, etc.) will be kept in a password-protected REDCap database on our secure network.

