# **Resources:**

The PI will oversee the study through weekly meetings to ensure proper study protocol adherence and recruitment and data progress. A study coordinator in the Pulmonary Division will conduct day to day activities of the study such as mailing of participant documents, data collection and input, and time points to send out materials. All mailing and data input will occur on Gonda 18 in the research laboratory.

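### Follow-up gait speed is hand-timed, and neither document names the tester or masks that person to arm, so the between-arm difference carried into R01 planning could include tester bias.

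*Protocol*

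**What the plan says.** **The test.** Under Study Measures in the Protocol, "gait speed will be measured using a stopwatch as the participant walks a distance of 15 feet at a self-selected walking speed". Gait speed is the mean of three trials. For the Short Physical Performance Battery (SPPB) the rule differs: "The best of 3 trials will be used to calculate the participant's SPPB score". The other SPPB parts are also timed. For chair stands, "The participant's SPPB score will be determined by the time required to complete 5 repeated chair stands". For balance, "Participants will be asked to hold each position for up to 10 seconds".

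**Who is retested.** Under Study Design and Methods, once the intervention is over, "all participants will be asked to complete a follow-up research visit in which they will complete the questionnaires, hand grip strength test, timed gait speed" and the remaining physical tests. This covers both arms.

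**Who does what.** Under Resources, "A study coordinator in the Pulmonary Division will conduct day to day activities of the study such as mailing of participant documents, data collection", together with data input and the timing of mailed materials. Coaching is a separate role: intervention participants are told that "they will be assigned a health coach trained in motivational interviewing who will call the patient weekly for 12 sessions". No section names the person who runs the physical tests.

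**When the arm becomes known.** Study Design and Methods places randomization during the baseline measures. Coached participants may take up to 16 weeks to finish their calls, whereas the control arm is described as 12 weeks of usual care. Study Measures ties retesting to the end of coaching in one arm and to a comparable interval in the other.

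**How the result is used.** The Protocol's Data Analysis section makes change in frailty parameters a secondary endpoint. The SAP lists between-group differences in change in gait speed as a secondary outcome for R01 planning and sets a two-tailed 0.05 significance level. SPPB, chair stands and balance are not in the SAP's list.

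**The concern.** A hand-timed walk at a pace the participant chooses depends on the tester in two ways: when the watch is started and stopped, and how the instruction and encouragement are given. If the tester knows the arm, either can differ between arms without anyone intending it. Participants in a coaching trial cannot be blinded, but for these tests the tester can be.

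The plan applies independence elsewhere: an outside expert monitors the recorded calls for treatment fidelity. Nothing comparable covers the outcome tests, and neither document mentions masking.

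The pilot exists to supply preliminary efficacy data for the power calculation of a larger study. If the gait-speed difference is inflated, an R01 sized on it will be too small.

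**Working it through.** **1. Is the tester masked?** Both documents were read for blinding, masking or an independent outcome assessor. None is mentioned. The only independent check is on the coaching calls.

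**2. Would the tester know the arm?** Three passages bear on this:
- Protocol, Resources: the only named data-collection role also runs day-to-day activities and the timing of materials.
- Protocol, Study Design and Methods: allocation happens while baseline measures are under way, so staff at that visit may learn it then.
- Protocol, Study Design and Methods and Study Measures: the follow-up date is set by the end of coaching in one arm and by an equivalent interval in the other, so whoever books the visit probably needs the arm.

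Together these make knowledge of the arm likely. None of them states it.

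**3. What reaches the comparison?** A timing error that is the same in both arms essentially cancels in a between-group difference of changes. Only a shift that differs by arm remains. Averaging three trials reduces random error but not a shift present in all three. The SPPB gait score takes the best trial, so one favourably timed walk is enough to affect it.

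**4. How large could it be?** The documents give no timing error and no gait speeds, so both are assumptions here.
- Distance: d = 15 × 0.3048 = 4.572 m (15 feet, from Study Measures).
- True walking time: T = d / v.
- Apparent gain from a time shortened by e seconds: Δv = d / (T − e) − v.

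| True speed v | T | e = 0.1 s | e = 0.2 s | e = 0.3 s |
|---|---|---|---|---|
| 0.8 m/s | 5.71 s | +0.014 | +0.029 | +0.044 |
| 1.0 m/s | 4.57 s | +0.022 | +0.046 | +0.070 |
| 1.2 m/s | 3.81 s | +0.032 | +0.066 | +0.103 |

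Entries are in m/s. Example: at 1.0 m/s with e = 0.2 s, 4.572 / 4.372 − 1.0 = 0.046 m/s. The range is about 0.01 to 0.10 m/s with no true change in walking.

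**5. What would it do to the significance test?** The SAP's own figure reproduces: 25 per group, effect size 0.81, two-sided 0.05, two-sample t-test gives 80.1% power (stated 80%). That calculation is for SMAS-30 and is not in dispute; it supplies the group size. With 25 per group, no true effect, and a tester shift expressed in SDs of the analysed change, the same noncentral-t calculation gives the chance of p < 0.05:

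| Shift (SD) | 0 | 0.1 | 0.2 | 0.3 | 0.5 |
|---|---|---|---|---|---|
| Chance of p < 0.05 | 5% | 6% | 11% | 18% | 41% |

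The documents give no SD for gait speed, so the two tables cannot be joined: no row of the first can be assigned to a column of the second.

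**The case against.** The strongest reply is that the point rests on silence in two brief documents. The stopwatch sentence shows only how gait is timed. A reader might infer that one coordinator handles all study contact, tests everyone and knows every allocation. The documents do not say so: a separate coach makes the calls, and the tester is unnamed. That part of the reply stands, and the claim is limited to what is missing and what is probable.

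Scope is the second reply. A reader might extend the point to chair stands and balance as tested outcomes, or to the trial's main result. The SAP lists only gait speed among these tests; SPPB enters only if it is reported under the Protocol's general heading of frailty parameters. Acceptability and feasibility do not depend on a stopwatch, and SMAS-30 is self-reported. This reply also stands.

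Third, the size is assumed. Nothing in the documents fixes the amount or even the direction of an arm-differential shift, so it cannot be said that the results are biased towards coaching, only that they could be. This stands.

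The reply does not remove the gap. A between-group gait comparison is planned, its result is meant to inform the R01, and no step keeps the arm from the person holding the watch.

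**Conclusion.** The concern holds for gait speed as an SAP secondary outcome, and conditionally for SPPB. The omission is established by the documents. That the tester knows the arm is a reasonable inference from the staffing and from arm-dependent follow-up timing. Bias is possible, not demonstrated.

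If an arm-differential shift of 0.1 to 0.3 s occurred, it would be worth about 0.01 to 0.10 m/s over the assumed speeds of 0.8 to 1.2 m/s. A shift of 0.2 SD would roughly double the false-positive chance, from 5% to about 11%. Both figures rest on assumed inputs. No sample-size figure changes and neither document's primary outcome is affected. It is a modest point, worth acting on because the remedy is cheap.

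**What to change.** With existing staff:

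1. Complete the baseline physical tests before the allocation is opened.
2. Have the health coach or the PI, not the tester, open the allocation, and give the tester only a follow-up date.
3. Hide the arm field from the tester's REDCap role.
4. Use scripted instructions for gait, chair stands and balance.
5. Ask participants not to mention coaching during testing, and record at the visit whether the arm was revealed.
6. Name the tester's role in the Protocol and state that it is masked to arm.

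If masking is not feasible, say so, report gait speed and SPPB as unmasked assessments, and do not use their between-group difference alone as the R01 effect size. Leading the frailty results with InBody is not a good substitute: Study Measures says that patients with a pacemaker or ICD cannot complete the scan, which would leave selective gaps in this population. Actigraph is more widely usable, but it records daily activity rather than tested gait.

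The cost is a REDCap permission change, a short test script, and a few Protocol sentences on the order of baseline testing, who holds the allocation and how follow-up dates are passed on. No added staff or procedures are needed. The downside is that some participants will still reveal their arm, particularly after up to 12 calls; recording this shows how often.
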